Randomization: The randomization of intervention sequence will be predetermined at the onset of the study and maintained by the study coordinator. At the time of consent, each participant will be assigned the randomly generated sequence of interventions.

Intervention: The study medication of carbidopa-levodopa and placebo will be prepared at the time of study initiation according to the randomization schedule. The intervention medication will be identified as drug 1-1, 1-2, 2-1, 2-2, 3-1, etc. according to the participant number and time period. The study medication and placebo will be obtained from the research pharmacy at Washington University in St. Louis. Each capsule of carbidopa-levodopa in this study will be equivalent to half of a standard carbidopa-levodopa 25/100mg tablet. Participants will take one capsule three times a day for the first week of the study period, increasing to two capsules three times a day for the remainder of the study period. Placebo capsules will be administered in the same way.

Measurement: The outcome measurements for this trial will be of subjective and objective measures of spasticity, pain, spasm, and functional capacity. The primary outcome of this study will be patient-reported symptoms on a numerical rating scale assessing spasticity severity. This scale will be administered at enrollment and weekly during the study.

Secondary outcomes measures of this study will be subjective and objective measures of pain, spasm, patient motor function, and spasticity. Participant symptoms of pain and spasm will be assessed via weekly administration of a numerical rating scale of pain and spasm. Patient strength and spasticity will be assessed on the MRC and Ashworth scale. Lower extremity function will be assessed by the Timed Up and Go (TUG) and 10 meter walk tests. These assays will be repeated twice at each study visit. Upper extremity function will be assessed by the 9 Hole Peg Test. This test will be repeated twice per arm at each visit. The Columbia Suicide Severity Rating Scale will be performed at enrollment, and repeated at each visit.

Blinding: As described above, the intervention sequence for each patient will be known only to the study coordinator. The participants and those evaluating the participants at each study visit will be blinded to the identity of the drug the participant has been taking.

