Participant Schedule Summary: Participation in this study will last for 6 weeks from the initial study visit. At the initial study visit, the participant's vital signs will be taken and the participant will undergo a neurological exam. Following this, the participant will complete the outcome measures as described above. The participant will leave with three weeks of the assigned study medication or placebo. At the end of each week, the participant will complete the spasticity, pain, and spasm numerical rating scales at home. At the end of the third week, the participant will return for a research visit where the exam and outcome measures will be repeated. The participant will cross over to the other treatment arm, and the above process will be repeated. After the second three week period, the participant will come in for a final assessment. At that point the participant's role in the study will be concluded. At each visit, potential side effects will be discussed. Over the course of the study, participants will be called by phone one week after the first visit and one week after the second visit to assess for side effects

Statistical analysis: The primary outcome data will be assessed for normality. If the data is normally distributed, analysis will be performed using ANOVA to compare the baseline and two treatment groups. Further testing for differences between groups will be carried out using the Paired-samples T-test. If the data is not normal, the non-parametric Kruskal-Wallis one way analysis of variance followed by the

Mann-Whitney U test will be used. As to the secondary variables, the data from the pain and spasm numerical rating scales will be analyzed like the spasticity data described above. The time data collected by the TUG, 10 meter walk, and 9 Hole Peg Tests will be analyzed via ANOVA, with further testing between groups performed by the Paired-samples T-test. The Ashworth scale and MRC will be compared between groups using Kruskal-Wallis one way analysis of variance followed by the Mann-Whitney U test as indicated. These non-parametric tests will be used as the Ashworth and MRC data will likely not be normally distributed.

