As for sample size, given the preliminary data, we expect the intervention to have a moderate to moderate-high effect. Thus with $\alpha=0.05$, power=0.07, and expected effect size of 0.7, the required sample size is 15 participants. This number is total given this is a paired analysis with the patients serving as controls for themselves.

Data Management:

Each participant will be given a coded ID number, and the spreadsheet containing the code correlating the patient's name with their study number will be kept on an encrypted, password-protected document (known only by members of the research team), which is behind the Washington University Department of Neurology firewall (accessible only by those with a department of Neurology account). Data collected during this study will be stored in RedCap.

Potential Benefits: In a case series of patients with ALS or PLS who have received carbidopa-levodopa at the Washington University School of Medicine Neuromuscle clinic, about one half have reported improvement in their symptoms of spasticity. These improvements have ranged from feeling less tightness, to improved gait and manual dexterity. Given the limitations of this data and the apparent ineffectiveness in some patients, no benefit is certain. Participants will be provided with a \$50 gift card for their time and effort. Parking validation will also be provided for study visits.

Potential Risks: The side effects most commonly associated with carbidopa-levodopa are diarrhea, orthostatic hypotension, and somnolence. Other rare adverse effects include hallucinations and dyskinesias. The dose of carbidopa-levodopa to be used in this study is commonly used in the Parkinson's disease patient population and is well tolerated. Additionally, the titration from the equivalent of one half of a 25/100mg tab to the equivalent of a full tab over a week should reduce the incidence of side effects.

Adverse Events: Participants in this study will be informed of the possible adverse effects of the medication and instructed to call the study coordinator if they begin to exhibit any of these symptoms. In particular, at each study visit and during the phone calls after the first and second study visits, the participants will be asked about symptoms of suicidal ideation, dyskinesia, and neuroleptic malignant syndrome among other possible side effects..All adverse events will be reviewed monthly by the study PI.

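### Vital signs are explicitly scheduled only before study drug is dispensed, and no visit specifies a standing blood pressure, although the protocol lists orthostatic hypotension among the commonest side effects

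*Combined protocol and SAP*

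**What the plan says.** The Participant Schedule Summary describes three visits.

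- **Initial visit.** "vital signs will be taken and the participant will undergo a neurological exam". The outcome measures follow, and then "The participant will leave with three weeks of the assigned study medication or placebo".
- **Week-3 visit.** "the participant will return for a research visit where the exam and outcome measures will be repeated".
- **Second period and final visit.** "The participant will cross over to the other treatment arm, and the above process will be repeated". Then "After the second three week period, the participant will come in for a final assessment".

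For safety at these visits the same section adds: "At each visit, potential side effects will be discussed". It also provides for two phone calls about side effects, one week after the first visit and one week after the second.

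The Measurement section sets the scope of the outcome measures: "The outcome measurements for this trial will be of subjective and objective measures of spasticity, pain, spasm, and functional capacity".

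The Potential Risks section states: "The side effects most commonly associated with carbidopa-levodopa are diarrhea, orthostatic hypotension, and somnolence". The Adverse Events section says that participants are told of possible adverse effects and asked to call if they develop them. For visits and calls it names three things to ask about (suicidal ideation, dyskinesia and neuroleptic malignant syndrome), with other side effects covered by a general phrase.

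**The concern.** The protocol identifies a common side effect that is defined by a measurement, the fall in blood pressure on standing, but does not explicitly schedule that measurement at any time. The blood pressure it does provide for, as part of vital signs, comes before the first dose.

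Three things follow if staff carry out the schedule as written.

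- A postural fall without symptoms, or with symptoms that the participant puts down to ALS or PLS, may go unrecorded.
- The population has weakness and spasticity, and performs the Timed Up and Go and the 10 meter walk at these same visits. A drop on standing matters both for safety and for understanding a poor walking result.
- A placebo-controlled crossover allows each participant's blood pressure on drug to be set against the same participant's blood pressure on placebo. That comparison is lost if the readings are not taken.

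The protocol already accepts structured safety assessment on treatment: it schedules the suicide severity scale at enrollment and at the end of each period because suicidal ideation is a potential serious side effect. It makes no similar provision for a side effect that it calls common.

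**Working it through.** The plan gives no figure on this point, and the point does not depend on alpha, power or effect size. The check is to compare the sections visit by visit.

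| Visit | Relation to study drug | What the text names | Vital signs named | Standing blood pressure named |
|---|---|---|---|---|
| Initial | Before dispensing | Vital signs, neurological exam, outcome measures | Yes | No |
| Week 3 | End of period 1 | Exam, outcome measures, side-effect discussion | No | No |
| Final | End of period 2 | A final assessment and side-effect discussion; the Design section adds objective data and the suicide scale | No | No |

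Counts: vital signs are explicitly scheduled at 1 of 3 visits and at 0 of 2 end-of-period visits. A standing blood pressure is explicitly scheduled at 0 of 3 visits.

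Four phrases could be read as bringing vital signs into the later visits.

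1. **The exam, at week 3.** The initial-visit sentence lists vital signs and the neurological exam as two items. The exam that is repeated most naturally means the second.
2. **Outcome measures.** The Measurement section lists numerical rating scales, MRC, Ashworth, Timed Up and Go, 10 meter walk, 9 Hole Peg Test and the suicide scale. None is a vital sign.
3. **Objective data, in the Design section.** The Measurement section gives this content as spasticity, pain, spasm and functional capacity, so it adds no blood pressure.
4. **Repeating the process after crossover.** Read loosely, this could add vital signs at the week-3 visit, because the process described above it starts with them. Participants who took carbidopa-levodopa first would then have a reading at the end of active treatment, and those who took placebo first would have one at the end of placebo. Each participant would have one end-of-period reading. A drug-placebo pair needs two, and the second depends on the final visit, whose content does not mention vital signs. No standing reading is added on this interpretation either.

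The remaining route is questioning. Each participant has two end-of-period visits and two calls at which side effects are raised, and may call in at other times. Under the Intervention section the capsule count rises after the first week, and each call comes about one week into a period. The next scheduled enquiry after the call is therefore the end-of-period visit. All of these routes rely on what the participant notices and reports.

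**The case against.** The strongest opposing case has four parts.

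**The text is a summary, and silence is not a zero.** This stands in part. A reader might infer that blood pressure is never measured on treatment, or count 0 readings at 30 end-of-period visits (15 participants x 2). The documents do not support that. The final visit is not itemised, the repeat-the-process sentence is loose, and staff may take vital signs routinely. What can be said is that such readings are not explicitly scheduled.

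**Side effects are actively asked about.** This also stands. A reader might infer that orthostatic hypotension is left to spontaneous report, which would be wrong: enquiry is planned at visits and by phone, and the general phrase in the Adverse Events section is wide enough to include orthostatic symptoms. What remains is that detection rests on participant report and that these symptoms are not named individually.

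**Listing a risk and monitoring it by questions are compatible.** Correct, in that no section promises a blood pressure reading on treatment, so this is not a strict contradiction. It is a gap between the risk statement and the visit schedule, and the two sections should be reconciled.

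**Repeating the initial-visit vital signs would not measure orthostatic hypotension.** Correct, because no standing reading is specified even at baseline. This widens the point: the missing item is a standing measurement at all three visits, as well as repetition at two. The cost must be counted over three visits.

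**Conclusion.** The point holds as a gap in the assessment schedule. Vital signs are explicitly scheduled only before study drug is dispensed, and no standing blood pressure is specified at any visit. Detection of a side effect that the protocol lists among the three commonest rests on participant report, and a within-participant comparison of blood pressure between drug and placebo is not assured.

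The conclusion assumes that the visit text is followed as written and that the exam means the neurological exam. If the sponsor intends vital signs at every visit, the later visits need only a clarification, but a standing reading would still have to be added.

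The consequence is limited to safety assessment. It does not alter the objectives, the primary outcome or its analysis. Nor does the point claim that the trial could establish a blood pressure effect: at most 15 participants would contribute pairs, fewer if any withdraw, and the documents give no standard deviation or threshold for blood pressure. They also do not state when a visit falls relative to the last dose. The change is worth making because it is cheap and specific.

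**What to change.** Reconcile the Participant Schedule Summary with the Potential Risks section.

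- List vital signs, with a standing blood pressure, among the assessments at the initial, week-3 and final visits, and itemise the final visit.
- In the Statistical analysis section, add a descriptive summary of these readings by treatment period, including each participant's drug-placebo difference. No hypothesis test or change to the sample size is needed.

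The cost is a few minutes at three visits already planned, with no new visit or staff. The change concerns assessment only and sets no dose, stopping or treatment rule. Any clinical response to a reading is for the sponsor and investigator to decide.

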Motivated by the success of dopaminergic drugs in treating rigidity associated with Parkinson's disease, some neurologists have used carbidopa-levodopa to attempt to improve spasticity in ALS and PLS patients. However, data on the efficacy of carbidopa/levodopa is limited. In unpublished data at this institution (Table 1) carbidopa-levodopa reduced spasticity and improved function in about half of the ALS and PLS patients that received the drug. Given the limited data and potential to improve the quality of life of these patients, the effectiveness of carbidopa-levodopa in ALS and PLS patients with severe spasticity should be studied. Our hypothesis is that administration of carbidopa-levodopa will improve spasticity in ALS and PLS patients.

Objectives

1. Determine the effect of carbidopa-levodopa on spasticity in ALS and PLS patients by a patient reported outcome measure.
2. Determine the effect of carbidopa-levodopa on objective motor function in patients with ALS and PLS.

Significance

ALS and PLS are neurodegenerative diseases of the motor tract that markedly reduce patients' function. In addition to the lack of curative therapies, there is a lack of symptomatic treatments. Spasticity is a key symptom of ALS and PLS that causes pain and limits patient function. The potential for carbidopa-levodopa to improve spasticity in these patients is intriguing. If carbidopa/levodopa is effective in reducing spasticity in these patients, they could have improvement in their functional status.

Research Plan

Design: This study is an interventional, placebo-controlled, single site, double-blind randomized crossover clinical trial. Identified participants will be randomized to receive either placebo or carbidopa-levodopa for a period of three weeks before crossing over to the other arm of the study. The two periods will be separated by a one day washout period. Below is a schematic showing examples of the randomized treatment periods. Where A represents a 3 week treatment period with carbidopa-levodopa and B represents a 3 week treatment period with placebo.

Participant 1: A->washout day->B

Participant 2: B->washout day->A

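### An unnamed normality check decides whether the primary comparison is paired or unpaired, although the 15 patients are justified by a paired analysis

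*Combined protocol and SAP*

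**What the plan says.** All references are to the combined protocol and SAP, Research Plan.

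- **Design:** "This study is an interventional, placebo-controlled, single site, double-blind randomized crossover clinical trial". Each patient takes both treatments.
- **Measurement:** "The primary outcome of this study will be patient-reported symptoms on a numerical rating scale assessing spasticity severity". The range and step of the scale are not given.
- **Statistical analysis, the switch:** "The primary outcome data will be assessed for normality". No test, threshold or time point is named, and within-patient differences are not mentioned.
- **Statistical analysis, if normal:** "If the data is normally distributed, analysis will be performed using ANOVA to compare the baseline and two treatment groups", and then "Further testing for differences between groups will be carried out using the Paired-samples T-test".
- **Statistical analysis, if not normal:** "If the data is not normal, the non-parametric Kruskal-Wallis one way analysis of variance followed by the" "Mann-Whitney U test will be used". No paired non-parametric test is offered.
- **Sample size** (the paragraph after Statistical analysis): "This number is total given this is a paired analysis with the patients serving as controls for themselves".

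The pain and spasm ratings follow the same route as the spasticity rating.

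**The concern.** A paired t-test works on the drug-minus-placebo difference within each patient, and needs only those differences to be roughly normal. Stable differences between patients, including a skewed spread of severity, cancel in the subtraction. A check on the scores can therefore fail for a reason that does the paired test no harm.

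In this plan a failed check changes more than the distributional assumption. It moves the analysis from a paired to an unpaired comparison, so the trial could lose the feature that justifies 15 patients. Because the check and its threshold are unnamed, the choice of branch is also left partly open until the data are in hand.

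**Working it through.** **Inputs from the documents.** Two-period crossover; alpha 0.05 (sidedness not stated); effect size 0.7; N = 15; paired basis. Power is printed as 0.07.

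**Inputs assumed, because the documents give none.** Whole-number 0-10 scale, mean 6, SD 2, within-patient correlation ρ varied, Shapiro-Wilk at 0.05 on the pooled scores. Only the final drug-placebo test is simulated; the three-condition ANOVA or Kruskal-Wallis step is left out.

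**1. Reproduce the plan's N.** For a two-sided paired t-test with d on the SD of the differences, the noncentrality is d√n = 0.7 × √15 = 2.711. With 14 df and critical value 2.145, power is 0.713. At n = 14 the same formula gives 0.678. So N = 15 is reproduced at power 0.70. The printed 0.07 taken literally gives n = 2, which is a separate error. One-sided alpha 0.05 with power 0.80 also gives 15. On either reading the calculation is paired.

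**2. What the unpaired test costs.** If scores have standard deviation SD and correlation ρ, the difference has SD × √(2(1−ρ)). A paired effect of 0.7 is therefore 0.7 × √(2(1−ρ)) in units of the score SD, which is all an unpaired test sees. It also ignores the correlation in its null distribution: with no effect, Mann-Whitney rejects in about 1% of trials at ρ = 0.5 and about 0% at 0.8.

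| ρ | Effect in score SDs | Mann-Whitney power, n = 15, continuous normal scores |
|---|---|---|
| 0 | 0.99 | 0.72 |
| 0.3 | 0.83 | 0.56 |
| 0.5 | 0.70 | 0.41 |
| 0.7 | 0.54 | 0.18 |
| 0.8 | 0.44 | 0.08 |

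For scale: two independent groups at d = 0.7 and power 0.70 need 2 × (1.960 + 0.524)² / 0.7² = 25.2, so 26 per group.

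**3. Power of the rule as written** (simulation under the assumptions above).

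| ρ | Rule as written | Paired t-test always |
|---|---|---|
| 0.3 | loss of 0.02 or less | about 0.70 |
| 0.5 | 0.63-0.66 | about 0.65-0.70 |
| 0.7 | 0.59 unskewed, 0.50 skewed | about 0.65-0.70 |
| 0.8 | 0.53 unskewed, 0.34 skewed | about 0.65-0.70 |

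A rough hand check for unskewed scores: at ρ = 0.7 about 21% of trials fail the check, and 0.79 × 0.68 + 0.21 × 0.18 = 0.575, near the simulated 0.59. At ρ = 0.8 about 25% fail, and 0.75 × 0.66 + 0.25 × 0.08 = 0.515, near 0.53.

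**4. Which part does the damage.**

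- *Keep the check on scores, replace Mann-Whitney with signed-rank:* power returns to 0.65-0.70.
- *Move the check to differences, keep Mann-Whitney:* power is 0.45-0.64 at ρ = 0.7 and about 0.46 at 0.8.
- *Unskewed whole-number scores:* a check on differences fails as often as one on scores, or more (0.21 v 0.21 at ρ = 0.7; 0.32 v 0.25 at 0.8).
- *Skewed patients at ρ = 0.7:* scores fail in about 48% of trials and differences in about 20%. Here the quantity checked matters.

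**5. Sensitivity.** Pooling the baseline scores into the check and assuming stronger skew gives, at SD 2, power of 0.62-0.64 (unskewed) and 0.57 (skewed) at ρ = 0.5, 0.48-0.49 and about 0.36 at 0.7, and 0.40 and 0.18 at 0.8. With that stronger skew, 88-99% of trials fail the check. With unskewed scores at SD 1.5, 62-76% fail, and even at ρ = 0.3 power drops from 0.682 to 0.602. In the other direction, continuous normal scores fail in only about 5-12% of trials.

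**The case against.** The strongest reply is that the fault lies in the unpaired fallback, and the check is incidental. Most of this stands. Step 4 shows that a paired fallback alone recovers nearly all the power with the check untouched. The loss reported here is therefore the same loss that any separate point on Kruskal-Wallis and Mann-Whitney would report. The two belong together, and the loss should be counted once. What survives is that, in the plan as written, the check decides whether that branch is reached.

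Three stronger readings are tempting, and the documents do not support them:

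- *That the plan definitely checks the wrong quantity.* A reader might infer this from the definition of the primary outcome. Scores are the most natural reading, but the text never says scores, pooled scores or differences. It is unspecified.
- *That whole-number ratings by themselves push the trial into the unpaired branch because scores are checked.* Differences of whole numbers are whole numbers too, and fail as often or more.
- *That choosing the test after seeing the data inflates the false-positive rate.* The rule and both branches are pre-specified, though the check is not, and no inflation was shown. Mann-Whitney is over-conservative on correlated scores.

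It is also fair to object that every power figure for the rule depends on a scale, SD, correlation, skew and normality test that the documents do not give, and that the omnibus step is omitted.

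**Conclusion.** The point holds in limited form. The plan makes pairing in its primary comparison conditional on an unspecified check, while its sample size takes pairing for granted. The unpaired branch causes the loss. The check controls access to it, and checking scores instead of differences worsens matters mainly when patients' scores are skewed.

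Diversion is a risk and not a certainty. In the main simulated setting the cost is small at correlation 0.5, roughly 0.1 to 0.2 in power at 0.7, and larger at 0.8 (0.34-0.53 against about 0.65-0.70). It is negligible at 0.3 or below in that setting, though not under every scale assumption. A crossover relies on appreciable within-patient correlation, so the costly range is the one its design counts on. The direction follows from the design; the size rests on the assumptions listed. With design power of only about 0.71 on the plan's own inputs, there is little to give away. The change should be made.

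**What to change.** Delete the normality check from the primary analysis and state, for example:

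> The primary analysis is the within-patient drug-minus-placebo difference in the spasticity numerical rating, tested by a paired method (paired t-test or its period-adjusted equivalent) whatever the distribution. The Wilcoxon signed-rank test is a sensitivity analysis.

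Use the same wording for the pain and spasm ratings, and name the time point whose ratings enter the difference. Moving the check to the differences while keeping Mann-Whitney is not enough, as step 4 shows.

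The cost is analysis wording only: no added patients, visits or data. In simulation the always-paired t-test kept its type I error at 0.04-0.06. The downside is slightly less power than the signed-rank test if the differences are heavy-tailed, and that test is still reported.

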SINEMET IN AMYOTROPHIC LATERAL SCLEROSIS AND PRIMARY LATERAL SCLEROSIS

Protocol Number: Sinemet-001

Sponsor: Washington University

Version 1.1, 03/13/2019

Project Title:

Carbidopa/levodopa for Spasticity in Amyotrophic Lateral Sclerosis and Primary Lateral Sclerosis Patients

Background

Amyotrophic lateral sclerosis (ALS) is a progressive neurodegenerative disease affecting motor neurons. Clinically, ALS manifests with lower motor neuron signs (weakness, atrophy, fasciculation) and upper motor neuron signs (weakness and spasticity). Primary lateral sclerosis (PLS) is similar, however it has only upper motor neuron manifestations. ALS can present initially in any body segment, with asymmetric limb weakness being the most common presentation. From initial presentation, the disease continues to progress to affect other limbs or bulbar (facial) musculature in a pattern without remissions or exacerbations. ALS eventually progresses to affect the respiratory and bulbar musculature leading to life-threatening respiratory failure and dysphagia (difficulty swallowing). The median survival time from diagnosis is 3-5 years. PLS follows a similar progression affecting various body sites, but generally progresses more slowly. Current treatments for ALS are limited, with only riluzole being shown to have effect on survival. Edaravone has been shown to slow functional deterioration in some ALS patients.

There is also a lack of symptomatic treatments for ALS and PLS patients. Spasticity in particular can become severe enough in some patients to be debilitating causing chronic pain and reducing patient's functional capacity. These patients can have limited response to medications currently indicated to treat spasticity such as baclofen and tizanidine.

Anecdotally, there is evidence levodopa, a precursor to dopamine, can improve spasticity in some ALS/PLS patients with severe spasticity. Carbidopa-levodopa (Sinemet), a combination medication that improves the efficacy of levodopa, is a mainstay of treatment of Parkinson's disease making it interesting that it might have an effect in ALS and PLS patients. In Parkinson's disease patients, carbidopa-levodopa markedly improved patients' rigidity. At the extreme spasticity that can be seen in ALS and PLS, spasticity and rigidity are difficult to distinguish.

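### The ANOVA pools the unrandomised baseline with drug and placebo, no contrast is named as deciding, and the two-period crossover has no period term

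*Combined protocol and SAP*

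**What the plan says.** The Design paragraph states: "This study is an interventional, placebo-controlled, single site, double-blind randomized crossover clinical trial". Each patient takes drug and placebo for three weeks each, in random order, with a one-day washout between. On allocation, the Randomization paragraph says "The randomization of intervention sequence will be predetermined at the onset of the study"; it does not mention blocking or an intended split.

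The primary outcome is a numerical rating of spasticity. Of its timing, the Measurement paragraph says "This scale will be administered at enrollment and weekly during the study". The baseline value is therefore the enrolment score, taken before any study treatment.

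For normal data, the Statistical analysis paragraph plans that "analysis will be performed using ANOVA to compare the baseline and two treatment groups", and then: "Further testing for differences between groups will be carried out using the Paired-samples T-test". Pain and spasm scores follow the same plan. The timed tests (TUG, 10 metre walk, 9 Hole Peg) "will be analyzed via ANOVA, with further testing between groups performed by the Paired-samples T-test". No sentence says which pair decides the trial, whether the t-tests depend on the ANOVA, whether the ANOVA is repeated-measures, or how period is handled.

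The sample-size text says "This number is total given this is a paired analysis with the patients serving as controls for themselves", without naming the pair.

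**The concern.** Three conditions give three possible pairs: drug–placebo, drug–baseline and placebo–baseline. Only the first compares randomised, blinded conditions. The other two, and the omnibus ANOVA that includes them, also respond to anything that changes between enrolment and follow-up. The outcome is patient-reported and patients are selected for clinically significant spasticity, so placebo response and regression to the mean are both plausible. With no deciding contrast named, a significant ANOVA or drug-versus-baseline test could be presented as efficacy. Disease progression would work against drug in that comparison.

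Two further effects bear on drug versus placebo itself. The order of the tests suggests, but does not state, that the ANOVA comes first as a gate; if so, it costs power. Second, any change between the two periods moves the paired difference one way in drug-first patients and the other way in placebo-first patients. Without a period term this adds variance, and with an unequal split it also shifts the estimate. The Background says of ALS that "the disease continues to progress to affect other limbs or bulbar (facial) musculature in a pattern without remissions or exacerbations", so some drift is possible, but the protocol gives no size for it over three weeks.

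**Working it through.** **Inputs.** From the protocol: n = 15, alpha 0.05, effect size 0.7, paired analysis. Assumed: two-sided testing; 0.7 is the mean paired difference divided by its SD; that SD is set to 1; equal correlation among the three conditions. All shifts below are assumptions in units of that SD.

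**The plan's own figure.** Paired t-test, noncentrality 0.7 × √15 = 2.711, 14 df, critical value 2.145: power 0.713. So 15 is the two-sided paired-t sample size for power 0.70. The printed power of 0.07 would need only 2 patients and is a separate error. One-sided testing at power 0.80 also gives 15. In each case the figure fits a two-condition paired test, not a three-condition ANOVA.

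**1. Drug equals placebo, both better than baseline** (simulation, 200,000 replicates; repeated-measures F on 2 and 28 df):

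| Improvement on baseline | ANOVA significant | Drug vs baseline favours drug, ungated | Same, gated by ANOVA | Drug vs placebo significant |
|---|---|---|---|---|
| 0.2 SD | 11% | 11% | 6.5% | 5% |
| 0.3 SD | 19% | 19% | 13% | 5% |
| 0.5 SD | 46% | 44% | 36% | 5% |

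Read instead as an ordinary one-way ANOVA (within-patient correlation 0.5), the F-test is significant in about 1.5%, 4% and 15%, and the gated drug-versus-baseline wins are about 1%, 3% and 13–14%. The ungated column does not depend on the type of ANOVA.

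**2. True effect 0.7, ANOVA used as a gate.** Ungated power is 0.71. With a repeated-measures gate it is 0.66 if placebo equals baseline and 0.61 if placebo is 0.3 SD worse than baseline; almost nothing is lost if placebo is at least 0.35 SD better. With an ordinary one-way gate and placebo equal to baseline it is about 0.38.

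**3. Period shift, no period term, scores worsening over time.** The paired difference has mean (effect + shift) in drug-first patients and (effect − shift) in placebo-first patients. With n₁ drug-first and n₂ placebo-first, the bias is shift × (n₁ − n₂)/15, and the expected sample variance rises by shift² × 4n₁n₂/(15 × 14). At 8:7 and a 0.5 shift that rise is 0.25 × 224/210 = 0.27.

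| Shift | Unadjusted power, 8 drug-first | Unadjusted power, 7 drug-first |
|---|---|---|
| 0.2 SD | 0.71 | 0.68 |
| 0.5 SD | 0.67 | 0.58 |

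The adjusted test compares within-patient period differences between sequences, with noncentrality 2 × 0.7/√(1/n₁ + 1/n₂) on 13 df. At 8:7 this is 1.4/√(1/8 + 1/7) = 2.705, power 0.706 whatever the shift. At 9:6 power is 0.690, and at 10:5 it is 0.657.

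**4. Unequal split, no drug effect.** With 10 drug-first and 5 placebo-first, the bias towards drug is 0.2 × 5/15 = 0.07 SD or 0.5 × 5/15 = 0.17 SD. False wins for drug are 3.9% or 6.0%, against a nominal 2.5%. The mirror split (5 drug-first) gives about 1.3% or 0.3%. Averaged over unrestricted 1:1 randomisation the rate is 2.5%. Under that scheme the chance of an 8:7 split in either direction is 0.39, and of 10:5 or worse in either direction 0.30.

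**The case against.** The strongest reply is that the valid test is already in the plan. The trial is placebo-controlled and blinded, the follow-up paired t-tests include drug versus placebo, the sample size is paired, and nothing says that a significant ANOVA or a change from baseline will count as efficacy. This stands in part: the right test is available and keeps its error rate. But it is one of three pairs with no order or priority, so the choice can be made after the results are seen.

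Second, the ANOVA is not described as repeated-measures, so the omnibus and gated figures rest on one reading. That is correct. The other reading gives far fewer false signals but makes a gate much more damaging to power, and the ungated drug-versus-baseline risk is the same under both.

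Third, the case for a period term rests on assumed shifts. This largely stands. Three weeks is short against a median survival of 3–5 years, and PLS is described as generally slower. At 0.2 SD with a near-even split the gain averages about one point of power; a material gain needs about 0.5 SD. The 10:5 bias is conditional on the split and goes either way, so it is not a general type I error defect. The period term is the lesser part of this point.

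**Conclusion.** The concern holds. The text includes an unrandomised baseline in the primary ANOVA, does not name drug versus placebo as the deciding comparison, and has no period term; nothing elsewhere in the protocol repairs this. The main consequence is that a positive result is undefined: with drug no better than placebo, drug-versus-baseline would favour drug in 11% to 44% of trials for assumed shared improvements of 0.2 to 0.5 SD. The secondary consequence is avoidable loss of power in a trial that has only about 0.71, through a gate if one is applied and through unmodelled period variation if it is large. The type I error of the ungated drug-versus-placebo t-test is not at issue on average. The sizes depend on the assumed shifts; the textual gap does not. The plan should be changed, but it is not invalid, since the valid test is among those listed.

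**What to change.** - State drug minus placebo as the single primary contrast, not conditional on any omnibus test. Report baseline descriptively.
- Estimate it from a crossover model with treatment and period as fixed effects and patient as a random effect, or equivalently by comparing within-patient period differences between the two sequences.
- Name in advance the one score per period that enters, for example the end-of-period score, because the scale is completed weekly.
- Use the same model for pain, spasm, TUG, 10 metre walk and 9 Hole Peg.
- If normality is rejected, apply the rank-sum test to the period differences between sequences, so that this branch is also within-patient and targets the same contrast. Its power at 8:7 is 0.64 whatever the period shift.
- Generate the sequence list in blocks so that the split stays close to 8:7.

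The cost is a rewritten paragraph and a blocked list. At 8:7 with no period effect the period term uses one degree of freedom and power goes from 0.713 to 0.706. Blocking and adjustment belong together: under unrestricted allocation, adjustment moves power from 0.71 to 0.68 with no shift and from 0.70 to 0.68 at 0.2 SD, and gains only at a larger shift (0.62 to 0.68 at 0.5 SD). A period term does not deal with carryover, which is a separate question.
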